7. STUDY OBJECTIVES

The endpoints for the objectives below are described in [Section 9.4.1](#) (efficacy), [Section 9.4.2](#) (safety), [Section 9.4.3](#) (PK), and [Section 9.4.4](#) (exploratory).

The overall study population is restricted to adults with NASH and stage 3 liver fibrosis. Qualifying participants will receive BMS-986036 for 48 weeks. See [Sections 8.3.1, 8.3.2, 8.3.3, and 8.3.4](#) for detailed inclusion and exclusion criteria, respectively.

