8.3.1 Inclusion Criteria

1. Signed written informed consent
 - a) Participants must be willing to participate in the study and sign the informed consent form(s) (ICF[s])
 - b) Participants (and caregivers as applicable) must be willing and able to complete all study-specific procedures and visits
2. Liver biopsy performed within 6 months (26 weeks) prior to the Screening Period. Biopsy performed prior to ICF must be available to the central reader prior to randomization. If historical biopsy is not available, a liver biopsy will be performed during the Screening Period (see [Section 8.5.1.1](#)). Biopsy must be consistent with NASH, with:
 - a) A score of at least 1 for each NAS component (steatosis, lobular inflammation, and ballooning), as assessed by the central reader
AND
 - b) Stage 3 liver fibrosis according to the NASH CRN classification, as assessed by the central reader
3. Participants taking anti-diabetic, anti-obesity, or anti-dyslipidemic medications must have been on stable regimens for at least 3 months (12 weeks) (6 weeks for statins) prior to and during the Screening Period. The investigator may contact the medical monitor regarding the stability of a participant's regimen when determining eligibility for study participation. Participants taking vitamin E at doses ≥ 800 IU/day must have been on stable doses for at least 6 months (26 weeks) prior to and during the Screening Period. Vitamin E treatment (≥ 800 IU/day) must not have been initiated after the qualifying liver biopsy was performed.

4. Age and reproductive status
 - a) Men or women 18 to 75 (inclusive) years of age
 - b) Women of childbearing potential (WOCBP) must have a negative pregnancy test (minimum sensitivity 25 IU/L or equivalent units of human chorionic gonadotropin) within 24 hours prior to the start of study medication
 - c) Women must not be breastfeeding at any time during the study
 - d) WOCBPs must agree to follow instructions for method(s) of contraception for the duration of treatment (BMS-986036 or placebo) plus 5 half-lives of study medication (5 days) plus 30 days (duration of ovulatory cycle) for a total of 35 days after the end of the Double-Blind Treatment Period
 - e) WOCBPs who are continuously not heterosexually active are exempt from contraceptive requirements but must undergo pregnancy testing as described in the Schedule of Activities in [Section 1](#)

[figure not shown]

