 - k) History of weight gain/loss $\geq 10\%$ of body weight within 6 months (26 weeks) prior to or during the Screening Period
 - l) Uncontrolled hypertension, as defined by systolic blood pressure (SBP) > 160 and/or diastolic blood pressure (DBP) > 100 during Screening, unless discussed with medical monitor. Blood pressure may be rechecked as clinically indicated
 - m) QT interval corrected using Fridericia's formula (QTcF) > 480 msec on 12-lead ECG during Screening, confirmed by repeat ECG 30-60 minutes after the initial ECG
 - n) Any acute or chronic cardiovascular condition (e.g., ischemic heart disease, congestive heart failure) considered clinically significant by the investigator
 - o) Known immunocompromised status, including but not limited to, individuals who have undergone organ transplantation, who are known to be positive for human immunodeficiency virus, or who have recurrent or chronic systemic bacterial, fungal, viral or protozoal infections
 - p) Major episode of infection requiring hospitalization within 4 weeks prior to or during the Screening Period
 - q) Inability to tolerate SC medication
 - r) Inability to tolerate venipuncture
 - s) Women who are breastfeeding
4. Prior and concomitant therapy
- a) Participants who have taken systemic corticosteroids at a dose exceeding 20 mg/day prednisone or equivalent for more than 7 consecutive days at any time within 3 months (12 weeks) prior to or during the Screening Period
 - b) Inability to comply with restrictions and prohibited treatments
 - c) Prior exposure to BMS-986036 or other FGF21 analogs
 - d) Other investigational agents must be discontinued at least 4 weeks or 5 half-lives before the first dose of study medication, whichever is longer
5. Physical and laboratory test findings
- a) Evidence of organ dysfunction or any clinically significant deviation from normal in physical examination, vital signs, or clinical laboratory determinations beyond what is consistent with the target population
 - b) ALT value $> 5 \times$ the upper limit of normal (ULN) as defined by the central laboratory
 - c) AST value $> 5 \times$ ULN as defined by the central laboratory
 - d) Total bilirubin > 1.5 mg/dL (unless the participant has a documented diagnosis of Gilbert's syndrome)
 - e) Serum albumin < 3.5 g/ dL
 - f) Platelet count $< 100 \times 10^3/\mu\text{L}$
 - g) International normalized ratio (INR) > 1.4 , unless due to therapeutic anticoagulation

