8.4.6.2 Dose Interruption

If a participant has abnormal laboratory test result(s) and/or clinical AE(s) that, in the judgment of the investigator, could place the participant at risk, study medication administration should be interrupted, and the investigator should notify the medical monitor. Participants may receive further study medication when the AE or abnormal laboratory finding is resolved.

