8.5.3 Safety Assessments

Planned time points for all safety assessments are listed in the Schedule of Activities (Section 1). All urgent safety concerns must be discussed with the sponsor immediately upon occurrence or awareness to determine if the participant should continue or discontinue treatment.

Safety will be assessed using incidence of all AEs; the incidence of SAEs; the incidence of AEs leading to withdrawal of study medication; the incidence of AEs of special interest, immunogenicity, laboratory data, ECG monitoring, physical examinations, and monitoring of BMD via DXA.

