8.5.3.1 Adverse Events

The definitions of an AE or SAE can be found in [Appendix 8](#).

AEs will be reported by the participant (or, when appropriate, by a caregiver, surrogate, or the participant's legally authorized representative).

The investigator and any designees are responsible for detecting, documenting, and reporting events that meet the definition of an AE or SAE and remain responsible for following up AEs that are serious, considered related to the study medication or the study, or that caused the participant to discontinue before completing the study.

For weight change (increase or decrease) to be considered an AE, the change should be 10% or more from Baseline that cannot be explained by lifestyle modifications alone.

Contacts for SAE reporting are specified in [Appendix 8](#).

Time Period and Frequency for Collecting AE and SAE Information

Sections 5.6.1 and 5.6.2 in the IB represent the Reference Safety Information to determine expectedness of SAEs for expedited reporting.

The collection of nonserious AEs should begin at initiation of study medication and continue until the Week 52/PTFU Visit ([Section 1](#)).

Following the participant's written consent to participate in the study, all SAEs, whether related or not related to study medication, must be collected, including those considered by the investigator to be related to study medication or protocol-specified procedures. All SAEs will be collected through the Week 52/PTFU Visit and will be reported as described in [Appendix 8](#).

The investigator must report any SAE occurring after the Week 52/PTFU Visit that is believed to be related to study medication or a protocol-specified procedure.

- Medical occurrences that begin before the start of study medication but after obtaining informed consent will be recorded on the appropriate section of the eCRF
- All SAEs will be recorded and reported to sponsor or designee within 24 hours, as indicated in [Appendix 8](#)
- The investigator will submit any updated SAE data to the sponsor or designee within 24 hours of this information being available

Investigators are not obligated to actively seek AEs or SAEs in former study participants. However, if the investigator learns of any SAE, including a death, at any time after a participant has been discharged from the study, and he/she considers the event reasonably related to the study medication or study participation, the investigator must promptly notify the sponsor.

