Any pregnancy that occurs in a female partner of a male study participant should be reported to sponsor or designee during at least 5 half-lives after product administration (5 days) plus 30 days (duration of ovulatory cycle) for a total of 35 days after the end of the Double-Blind Treatment Period. In order for the sponsor or designee to collect any pregnancy surveillance information from the female partner, the female partner must sign an ICF for disclosure of this information. Information on this pregnancy will be collected on the Pregnancy Surveillance Form.

Laboratory Test Result Abnormalities

The following laboratory test result abnormalities should be captured on the nonserious AE eCRF page or SAE eCRF page, as appropriate. Paper forms are to be used only in the event that the electronic system is not functioning.

- Any laboratory test result that is clinically significant or meets the definition of an SAE
- Any laboratory test result abnormality that required the participant to have study medication discontinued or interrupted
- Any laboratory test result abnormality that required the participant to receive specific corrective therapy

It is expected that wherever possible, the clinical rather than laboratory term would be used by the reporting investigator (e.g., anemia versus low hemoglobin value).

Potential Drug-Induced Liver Injury

Wherever possible, timely confirmation of initial liver-related laboratory abnormalities should occur prior to the reporting of a potential DILI event. All occurrences of potential DILIs, meeting the defined criteria, must be reported as SAEs (see Appendix 8 for reporting details). **Repeat laboratory testing may be performed locally**, and the results should be promptly communicated to the investigator site.

For the purpose of evaluating a potential DILI, the Baseline value is defined as the mean of the test results from analysis of samples collected during Screening and on Day 1.

Note that the evaluation processes below do not replace SAE reporting per defined criteria in [Appendix 8](#).

Evaluation of Participants with New Elevations of Aminotransferases and/or Total Bilirubin

Repeat laboratory testing (including ALT, AST, fractionated bilirubin and alkaline phosphatase) and physical examination should be performed within 48-72 hours when:

- Participants with normal Baseline aminotransferase (ALT and/or AST) values develop elevations greater than $3\times$ the ULN based upon the central lab, or

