Is an important medical event (defined as a medical event(s) that may not be immediately life-threatening or result in death or hospitalization but, based upon appropriate medical and scientific judgment, may jeopardize the participant or may require intervention [e.g., medical, surgical] to prevent one of the other serious outcomes listed in the definition above); examples of such events include, but are not limited to, intensive treatment in an emergency room or at home for allergic bronchospasm; blood dyscrasias or convulsions that do not result in hospitalization.
Wherever possible, timely confirmation of initial liver-related laboratory abnormalities should occur prior to the reporting of a potential DILI event. All occurrences of potential DILIs, meeting the defined criteria, must be reported as SAEs.
Potential DILI is defined as: 
• ALT or AST $> 3 \times$ ULN AND• Total bilirubin $> 2 \times$ ULN, without initial findings of cholestasis (elevated serum alkaline phosphatase) AND• No other immediately apparent possible causes of ALT or AST elevation and hyperbilirubinemia, including, but not limited to, viral hepatitis, pre-existing chronic or acute liver disease, or the administration of other drug(s) known to be hepatotoxic

Suspected transmission of an infectious agent via the study medication is an SAE.

Although pregnancy, overdose, cancer, and potential DILI are not always serious by regulatory definition, these events must be handled as SAEs.

Evaluating AEs and SAEs

Assessment of Intensity
The intensity of AEs is determined by a physician and will use the following level:

• Mild: An event that is easily tolerated by the participant, causing minimal discomfort, and not interfering with everyday activities• Moderate: An event that causes sufficient discomfort and interferes with normal everyday activities

- Severe: An event that prevents normal everyday activities. An AE that is assessed as severe should not be confused with an SAE. Severe is a category utilized for rating the intensity of an even; and both AEs and SAEs can be assessed as severe.

Assessment of Causality

The causal relationship to study medication is determined by a physician and should be used to assess all AEs. The causal relationship can be one of the following:

Related: There is a reasonable causal relationship between study medication administration and the AE.

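### The potential-DILI definition counts pre-existing chronic liver disease as another cause without exempting the NASH every participant has, so a joint ALT/AST and bilirubin elevation could miss the mandatory 24-hour SAE report

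*Protocol*

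**What the plan says.** Protocol Section 8.5.3.1 states the rule: "All occurrences of potential DILIs, meeting the defined criteria, must be reported as SAEs". It also sets the clock: "All SAEs will be recorded and reported to sponsor or designee within 24 hours".

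The defined criteria are in Protocol Appendix 8, and all three must hold:

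1. ALT or AST above 3x ULN.
2. Total bilirubin above 2x ULN, without initial signs of cholestasis.
3. No other possible cause of the aminotransferase elevation and hyperbilirubinemia that is apparent straight away, "including, but not limited to, viral hepatitis, pre-existing chronic or acute liver disease", or another hepatotoxic drug.

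On who is enrolled, Protocol Section 7 says: "The overall study population is restricted to adults with NASH and stage 3 liver fibrosis". Inclusion criterion 2b requires "Stage 3 liver fibrosis according to the NASH CRN classification, as assessed by the central reader".

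**The concern.** The third criterion reads as if written for people without liver disease. In this trial the named exception describes the condition that qualifies a person for entry. An investigator who follows the text could attribute a joint elevation to NASH, conclude that the definition is not met, and not file the report.

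Appendix 8 itself acknowledges that potential DILI is not always serious by the regulatory definition and requires it to be handled as an SAE anyway. The special rule therefore exists for cases that the general seriousness criteria may not catch, and those are the cases the exception could remove. What is at stake is the speed and certainty of expedited reporting for a liver-safety signal. No efficacy endpoint or analysis is affected.

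**Working it through.** The plan states no figure on this point, so the check sets the provisions side by side.

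**Step 1. Where the decision falls.** Take an illustrative participant with ALT 4.5x ULN, bilirubin 2.2x ULN and normal alkaline phosphatase. Since 4.5 > 3 and 2.2 > 2 without cholestasis, criteria 1 and 2 are met. Whether the 24-hour report is mandatory then depends entirely on criterion 3.

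**Step 2. Does NASH fit the exception?** It is chronic and present before treatment in every participant. Exclusion criterion 1 (Section 8.3.2) removes most other chronic liver diseases: alcoholic, hepatitis B, chronic hepatitis C, autoimmune, drug-induced, Wilson disease and others. Among those enrolled, the chronic liver disease the phrase can mainly describe is the study disease.

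**Step 3. Could NASH account for both halves?**
- *Aminotransferases.* Entry is barred only above 5 times "the upper limit of normal (ULN) as defined by the central laboratory". Since 5 > 3, a participant can meet criterion 1 at baseline with no rise at all. NASH is a ready explanation for this half.
- *Bilirubin.* Entry is barred above 1.5 mg/dL unless Gilbert's syndrome is documented. A value at that limit exceeds 2x ULN only if the ULN is below 1.5 / 2 = 0.75 mg/dL. The documents do not give the ULN. For any ULN of 0.75 mg/dL or more, bilirubin above 2x ULN is a new rise in a participant without Gilbert's syndrome. Section 8.3.2 also excludes decompensation, varices, albumin below 3.5 g/dL, INR above 1.4 (unless due to anticoagulation) and significant worsening of liver tests in screening. Stable stage 3 NASH is therefore a poor explanation for this half.
- *Standard of proof.* Criterion 3 asks only for a possible cause. Progression to cirrhosis at Week 24 is a secondary endpoint (Section 9.4.1.2), so the plan allows that the disease may worsen on study.

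**Step 4. Is there an exemption elsewhere?** None appears in either document. The DILI work-up in Section 8.5.3.1 gives examples of competing etiologies (alcohol use, viral hepatitis, biliary obstruction, autoimmune liver disease) that do not include NASH, but that list governs the work-up and not the SAE definition. The two standards also differ: restarting drug requires an alternative cause to be definitively identified, while staying outside the SAE definition requires only a possible one. SAEs are otherwise reportable whether related or not, so criterion 3 puts a causality judgement ahead of the report.

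**Step 5. Does another route guarantee the 24-hour report?**

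| Route | Place | Why it does not |
|---|---|---|
| General SAE criteria, including important medical event | Appendix 8 | Same 24-hour clock, but the event must be judged serious |
| Recording clinically significant laboratory results | Section 8.5.3.1 | May go on the nonserious AE page |
| Retest and stopping rules | Section 8.5.3.1 | Stated not to replace SAE reporting; medical-monitor contact is within 48-72 hours |
| Dose interruption | Section 8.4.6.2 | Applies to findings that, "in the judgment of the investigator, could place the participant at risk, study medication administration should be interrupted" |
| Urgent concerns | Section 8.5.3 | "All urgent safety concerns must be discussed with the sponsor immediately upon occurrence or awareness", but someone must first see the event as urgent |
| Sponsor and DMC monitoring | Section 6.3.3 | Review of accumulating data, not a report of each case |
| Joint-elevation category and DILI graph | SAP 4.3.5 and 6.2.1 | Analysis summaries |

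None of them makes a joint elevation, as such, a mandatory 24-hour report.

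**The case against.** The best counter-argument is that the gap needs a strained reading. Criterion 3 links aminotransferase elevation and hyperbilirubinemia with an "and", so a qualifying cause should explain both, and Step 3 shows that stable stage 3 NASH does that badly. The work-up examples suggest that NASH was not meant as a competing cause. A careful investigator would probably report the event, either as potential DILI or as an important medical event. This stands as a limit on likelihood. It does not amend the definition, which still names the category into which every participant falls and asks only for a possible cause.

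It can also be said that an amended criterion would still turn on judgement, because another apparent cause could still be invoked. That is true. The gain is that the one cause present in everybody would no longer be available.

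A reader might go further and infer that no participant can ever meet the definition, or that liver signals would be lost. The documents support neither. On the conjunctive reading, cases still qualify. Joint elevations are also tabulated under SAP 4.3.5 whatever their cause, and the sponsor and the DMC monitor safety throughout.

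**Conclusion.** The concern holds in limited form: read literally, the third potential-DILI criterion allows the study disease to be used to withhold the mandatory 24-hour report of a joint elevation, and nothing in either document prevents it. The gap is in guaranteed expedited reporting and not in detection. It is a cheap improvement, not a flaw that threatens the trial's conclusions.

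Its size cannot be computed. The documents give no baseline ALT/AST distribution, no expected number of joint elevations, and no basis for how often an investigator would cite NASH. A reader might try to size it from the thresholds in Section 8.5.3.1, since the elevated-baseline retest rule and the first stopping scenario both require more than 2x Baseline and can stay silent at lower rises. That would measure where those rules are silent, which is a different question, because they are not reporting rules.

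The conclusion rests on two readings: that NASH falls within the ordinary meaning of pre-existing chronic liver disease, and that a merely possible cause is enough under the text.

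**What to change.** Add one clause to the third criterion in Appendix 8: the participant's underlying NASH with stage 3 fibrosis is not by itself an alternative cause. Confirmed joint elevations without cholestasis or another apparent cause are then reported as SAEs, and causality is assessed afterwards.

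The cost is one clause and possibly a few more expedited reports. Some of these may come from participants whose ALT/AST is stable above 3x ULN, for whom a bilirubin rise alone completes the laboratory criteria. No condition requiring a rise above a multiple of baseline is proposed. The documents give no basis for choosing a multiple, and such a condition could narrow the reporting that the clause is meant to protect.

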Appendix 9 Formulae for Measurements

- ELF assay combines hyaluronic acid, procollagen 3 amino terminal peptide, and tissue inhibitor of metalloproteinase 1. An algorithm is used to evaluate each of these markers by immunoassay, to create an ELF Score.
- FIB4 score (age [years] \times AST level [U/L])/(platelet count [$\times 10^9/L$] \times square root of ALT [U/L])
- APRI score ([AST divided by AST Upper Limit of Normal]/platelet count [$\times 10^9/L$]) \times 100
- NAFLD Fibrosis Score $-1.675 + 0.037 \times \text{age (years)} + 0.094 \times \text{BMI (kg/m}^2\text{)} + 1.13 \times \text{fasting glucose/diabetes (yes 1, no 0)} + 0.99 \times \text{AST/ALT ratio} - 0.013 \times \text{platelet count} - 0.66 \times \text{albumin (g/dL)}$

[figure not shown]
Method of BMI Calculation:

- Use actual height and weight collected on the same day. Whenever possible, body weight should be measured using the same scale throughout the study.
- To calculate BMI:
 - Convert weight pounds to kg (kg = pounds/2.2)
 - Convert height inches to centimeters (cm = inches \times 2.54)
 - BMI = (weight in kg)/(height in cm/100) 2
 - Round to 1 decimal place (if 0.05 or greater, round up)

Appendix 10 Decision Tree for Long-Term Immunogenicity Follow-Up Visits After the Week 52/PTFU Visit

Participants who discontinue study medication prior to Week 48 are expected to complete an ET Visit and to remain in the study and continue to have immunogenicity monitored according to the Schedule of Events in [Section 1](#).

Participants who discontinue study participation will be offered immunogenicity follow-up visits, as per the diagram. All participants will have immunogenicity samples collected at 6 months after the Week 52/PTFU Visit. Additional immunogenicity follow-up visits may occur approximately 9, 12, and 14 months, if applicable, (visit window \pm 14 days) (1 month is defined as 4 calendar weeks) after the last completed study visit.

FU = Follow-Up; IMG = Immunogenicity (anti-drug and anti-FGF21 antibodies); Mo = month (defined as 4 calendar weeks)

^a All participants will have samples collected for immunogenicity at 6 months (\pm 14 days) after the Week 52/PTFU Visit. Samples collected from participants may not be analyzed if: 1) participant is not on active drug, 2) participant is negative for anti-drug and/or anti-FGF21 antibody titers at the Week 52/PTFU Visit, or 3) participant has evidence of stable or decreasing antibody titers for 2 visits prior to the 6-month posttreatment visit.

^b Additional assessments include: basic metabolic panel, hemoglobin A1c, [REDACTED]
